6.4.2. Hypothesis Testing Strategy for Immunogenicity

The hypothesis tests for noninferiority, superiority, and "super" superiority of mRNA-1273.214 against Omicron as compared to mRNA-1273 primary series against Omicron will be performed sequentially. The noninferiority hypotheses (hypotheses HA¹ and HA²) will be tested first.

Once noninferiority is demonstrated based on both GMC or GM level and SRR, superiority (hypotheses $\rm HA^3$ and $\rm HA^4$) of mRNA-1273.214 as compared to mRNA-1273 primary series will be tested. If the lower bound of the 95% CI of the GMR is > 1, superiority based on GMC or GM level is demonstrated; if the lower bound of the 95% CI of the SRR difference is > 0%, superiority based on seroresponse is demonstrated.

Once superiority is demonstrated based on both GMC or GM level and SRR, "super" superiority (hypotheses HA⁵ and HA⁶) of mRNA-1273.214 as compared to mRNA-1273 primary series will be tested. If the lower bound of the 95% CI of the GMR is > 1.5, "super" superiority based on GMC or GM level is demonstrated; if the lower bound of the 95% CI of the SRR difference is > 10%, "super" superiority based on seroresponse is demonstrated.

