6.4.3. Primary Analysis of Antibody-Mediated Immunogenicity Endpoints

For Part 2, the immune response as measured by the serum Ab GM value and SRR against SARS-CoV-2 VOC (Omicron) at 28 days after the second dose of mRNA-1273.214 will be compared to that of the young adult participants (18-25 years) at 28 days after the second dose of mRNA-1273 primary series in Study mRNA-1273-P301.

An analysis of covariance (ANCOVA) model will be carried out with the serum Ab value at 28 days after the second dose of IP (Day 85 for Study P206, Day 57 for Study P301) as the dependent variable and a group variable (mRNA-1273.214 vs. mRNA-1273) as the fixed variable, adjusted by the baseline serum Ab value. The serum Ab GM value at Day 85 for Study P206 and serum Ab GM value at Day 57 for Study P301 will be estimated by the geometric least square mean (GLSM) from the model. The GMR (Study P206 vs. Study P301) will be estimated by the ratio of GLSM. Its 2-sided 95% CI will also be provided to assess the difference in immune response between the Study P206 and Study P301 at 28 days after the second dose of IP.

The noninferiority of the GM value of mRNA-1273.214 compared with mRNA-1273 primary series will be demonstrated if the lower bound of the 95% CI of the GMR > 0.667.

In addition, the serum Ab GM value with its 95% CI and GMR with 95% CI will be provided at 28 days after the second dose of IP. The 95% CIs will be calculated based on the t-distribution of the log-transformed values then back transformed to the original scale. Descriptive summary statistics for serum Ab values including median, minimum, and maximum will also be provided.

The GMFR of serum Ab values with its 95% CI at 28 days after the second dose of IP over baseline (pre-Dose 1 of primary series) will be provided. Its 95% CIs will be calculated based on the t-distribution of the log-transformed values then back transformed to the original scale for presentation.

The number and percentage of participants with seroresponse due to vaccination will be provided with 2-sided 95% CI using Clopper-Pearson method at 28 days after the second dose of IP, where seroresponse at subject level is defined two ways:

- 1. as an Ab value change from baseline (pre-Dose 1 of primary series) below the LLOQ to $\geq 4 \times \text{LLOQ}$, or at least a 4-fold rise if baseline is $\geq \text{LLOQ}$.

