- 2. as an Ab value change from baseline (pre-Dose 1 of primary series) below the LLOQ to \geq 4 × LLOQ, or at least a 4-fold rise if baseline is \geq LLOQ and <4 × LLOQ, or at least a 2-fold rise if baseline is \geq 4 × LLOQ.

The SRR difference with its 95% CI (using Miettinen-Nurminen score method) between pediatric participants receiving mRNA-1273.214 in Study P206 at Day 85 and adult participants receiving mRNA-1273 primary series in Study P301 at Day 57 will be provided.

The noninferiority of the SRR of mRNA-1273.214 compared with that of mRNA-1273 primary series will be demonstrated if the lower bound of the 95% CI of the SRR difference is > -5%.

The table below lists possible scenarios of GMR and SRR difference results and corresponding immunogenicity hypothesis testing conclusions.

Endpoints	Scenario		Conclusion
GMC or	1	Lower bound of 95% CI of GMR (GMC _{P206} /	Non-inferiority of mRNA-1273.214 in P206
GM level		GMC_{P301} or GM level _{P206} / GM level _{P301}) \leq	as compared to mRNA-1273 100 µg primary
Ratio		0.667	series (PS) in P301 based on GMR is not
			demonstrated

	3	$0.667 < Lower bound of 95\% CI of GMR$ $(GMC_{P206}/GMC_{P301} \text{ or } GM \text{ level}_{P206}/GM$ $level_{P301}) \leq 1$ $1 < Lower bound of 95\% CI of GMR$ $(GMC_{P206}/GMC_{P301} \text{ or } GM \text{ level}_{P206}/GM$	Non-inferior of mRNA-1273.214 in P206 as compared to mRNA-1273 100 µg PS in P301 based on GMR is demonstrated but superiority is not demonstrated. Superiority of mRNA-1273.214 in P206 as compared to mRNA-1273 100 µg PS in P301 based on GMR is demonstrated but "super"
	4	$ evel_{P301}) \le 1.5$ $Lower bound of 95\% CI of GMR$ $(GMC_{P206}/GMC_{P301} or GM evel_{P206}/GM $ $ evel_{P301}) > 1.5$	superiority is not demonstrated "Super" superiority of mRNA-1273.214 in P206 as compared to mRNA-1273 100 μg PS in P301based on GMR is demonstrated
SRR Difference	1	Lower bound of 95% CI of SRR difference $(SRR_{P206} - SRR_{P301}) \le -5 \%$	Non-inferiority of mRNA-1273.214 in P206 as compared to mRNA-1273 100 µg PS in P301 based on SRR difference is not demonstrated
	2	-5% < Lower bound of 95% CI of SRR difference (SRR _{P206} - SRR _{P301}) \leq 0	Non-inferiority of mRNA-1273.214 in P206 as compared to mRNA-1273 100 µg PS in P301 based on SRR difference is demonstrated but superiority is not demonstrated

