	3	0 < Lower bound of 95% CI of SRR difference (SRR _{P206} - SRR _{P301}) $\leq 10\%$	Superiority of mRNA-1273.214 in P206 as compared to mRNA-1273 100 µg PS in P301 based on SRR difference is demonstrated but "super" superiority is not demonstrated
	4	Lower bound of 95% CI of SRR difference $(SRR_{P206} - SRR_{P301}) > 10\%$	"Super" superiority of mRNA-1273.214 in P206 as compared to mRNA-1273 100 µg PS in P301 based on SRR difference is demonstrated

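### The conclusion table in SAP 6.4.3 drops the both-endpoints condition of SAP 6.4.2, so six of the 16 GMR-by-SRR outcomes print a claim that 6.4.2 bars

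*SAP*

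**What the plan says.** SAP 6.4.2 sets a three-step sequence. Noninferiority on the GMR (HA1) and on the SRR difference (HA2) comes first. The second step opens with "Once noninferiority is demonstrated based on both GMC or GM level and SRR, superiority" (HA3 for GMR, HA4 for SRR). The third opens with "Once superiority is demonstrated based on both GMC or GM level and SRR" ('super' superiority: HA5 for GMR, HA6 for SRR). Protocol 9.5.1 has the same two gates.

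SAP 6.4.3 ends with a table introduced by "The table below lists possible scenarios of GMR and SRR difference results and corresponding immunogenicity hypothesis testing conclusions". It has four rows for the GMR, cut at lower limits of 0.667, 1 and 1.5, and four for the SRR difference, cut at -5%, 0 and 10%. The conclusion in GMR row 3 begins "Superiority of mRNA-1273.214 in P206 as compared to mRNA-1273 100" and goes on "PS in P301 based on GMR is demonstrated". The SRR rows use the parallel wording "PS in P301 based on SRR difference is demonstrated". No row mentions the other endpoint or refers back to 6.4.2.

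**The concern.** The two SAP sections give different answers to the same question. Under 6.4.2, a GMR lower limit above 1 supports a superiority claim only if both noninferiority tests have succeeded. Under the table, the same limit is enough by itself. A report written from the table could state superiority on one endpoint after the other co-primary had failed. It could also state 'super' superiority when superiority had not been shown on both. The rule in SAP Section 1 that the SAP prevails over the protocol does not help, because the conflict lies within the SAP.

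**Working it through.** **Counting the outcomes.** Number the rows 1 to 4 for each endpoint. Section 6.4.2 permits superiority only if both endpoints are in row 2 or higher, and 'super' superiority only if both are in row 3 or higher. Of the 4 × 4 = 16 pairs, ten agree with the table and six do not:

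| GMR row | SRR row | Table prints | 6.4.2 permits for that endpoint |
|---|---|---|---|
| 3 | 1 | GMR superiority | GMR noninferiority |
| 4 | 1 | GMR 'super' superiority | GMR noninferiority |
| 1 | 3 | SRR superiority | SRR noninferiority |
| 1 | 4 | SRR 'super' superiority | SRR noninferiority |
| 4 | 2 | GMR 'super' superiority | GMR superiority |
| 2 | 4 | SRR 'super' superiority | SRR superiority |

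Pairs (1,2) and (2,1) are not counted. Section 6.4.2 puts no gate between HA1 and HA2, and 6.4.3 defines noninferiority endpoint by endpoint ("The noninferiority of the GM value of mRNA-1273.214 compared with mRNA-1273 primary series will be demonstrated if the lower bound"; "The noninferiority of the SRR of mRNA-1273.214 compared with that of mRNA-1273 primary series will be demonstrated if the lower bound").

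**Inputs for frequency.** SAP 4.3 gives 250 evaluable infants, SD 1.0 on the natural log scale, true GMR 1, adult SRR 60-70%, infant SRR 10 points higher and two-sided alpha 0.05. The adult number is not given; 250 is assumed, with 1,000 as an alternative. The correlation between the two estimates is not given either; 0 to 0.9 is used.

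**Formulas.** SE(log GMR) = √(1/250 + 1/250) = 0.0894. SE(SRR difference) = √(p₁(1−p₁)/250 + p₂(1−p₂)/250), which is 0.0424 for 70% v 60% and 0.0385 for 80% v 70%. For true value θ and cut c, P(lower limit ≤ c) = Φ((c − θ)/SE + 1.96).

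**The plan's own figure.** Noninferiority power is 99.5% for the GMR and 94.2% (adult SRR 60%) to 97.4% (70%) for the SRR difference. These agree with the stated minimum of 90%.

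**Planning point, zero correlation.** Row probabilities, rows 1 to 4:
- GMR: 0.0051, 0.9699, 0.0250, 0.0000
- SRR, adults 60%: 0.0576, 0.2881, 0.6293, 0.0250
- SRR, adults 70%: 0.0262, 0.2350, 0.7137, 0.0250

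For adults at 60%:
- SRR row 3 or 4 with GMR row 1: 0.0051 × (0.6293 + 0.0250) = 0.0033
- SRR row 4 with GMR row 2: 0.9699 × 0.0250 = 0.0242
- GMR row 3 with SRR row 1: 0.0250 × 0.0576 = 0.0014
- Total: about 0.029 (also 0.029 for adults at 70%)

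A bivariate normal simulation (2,000,000 draws per setting) over correlations 0 to 0.9 gives 1.0-2.9%. Superiority after the other co-primary failed accounts for 0-0.5%, and SRR 'super' superiority with HA3 unmet for 1.0-2.4%.

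**Away from the planning point.** These true values are assumed; none is in the documents.

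| True GMR | True SRR difference | Barred claim | 250 adults | 1,000 adults |
|---|---|---|---|---|
| 1.5 | 0 | GMR superiority, HA2 failed | 77-79% | 66-70% |
| 2.0 | +10 points | GMR 'super' superiority, HA4 unmet | 16-31% | 5-14% |
| 1 | +20 points | SRR 'super' superiority, HA3 unmet | 68-80% | about 90-96% |

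Hand check of the first line, adults 60%, zero correlation: P(GMR lower limit > 1) = Φ(0.4055/0.0894 − 1.96) = 0.995. P(HA2 fails) = 1 − Φ(0.05/0.0438 − 1.96) = 0.794. The product is 0.79. At the planning point with 1,000 adults the total is 1.0-2.5%.

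A patient-level simulation with t-based GMR intervals and Miettinen-Nurminen limits (40,000 trials per setting, 250 per group) agrees: 76-79%, 19-31% and 67-80% for the three lines.

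**The case against.** The best defence is that 6.4.2 comes immediately before 6.4.3, is headed as the testing strategy and is nowhere revoked. It also states the superiority thresholds endpoint by endpoint, inside sentences that the gate has already opened. On that reading the table only restates those thresholds, and what is missing is a cross-reference. The reading is possible, but the table does not state it. It keeps the thresholds, drops the gate and says without condition that a hypothesis is demonstrated.

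Three further points limit the weight of the concern:
- The table has eight rows and never crosses them; the 16 outcomes follow from applying both halves to one trial.
- The planning-point frequency is small, the co-primary tests are untouched, and SAP Section 7 reports an enrollment pause, so the matter depends on Part 2 being run.
- The large percentages use assumed pairs of true values. GMR and SRR come from the same antibody values. With SD 1 in both groups and baselines below LLOQ (an assumption), a GMR of 1.5 would imply an SRR gain of Φ(0.253 + 0.405) − 0.60 ≈ 15 points when the adult rate is 60%, or about 12 points when it is 70%.

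The last point lowers the weight of those scenarios without removing it. Seroresponse depends on rise from baseline, and the protocol expects maternal antibody at this age, so high infant titers with a weak SRR are plausible. That mechanism works against the GMR 1, +20 case. The SAP's own planning pair, GMR 1 with +10 points, is discordant under the same simple model.

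**Conclusion.** The table is wrong as written. It is a stated decision rule that contradicts SAP 6.4.2 and Protocol 9.5.1 in six of 16 outcomes, and that count needs no assumptions. How often it would matter depends on the unstated adult number, the correlation and the true effects: 1.0-2.9% of trials at the planning values with 250 per group, and from 16% up to 80% in the divergent scenarios tried. Only the secondary claims HA3 to HA6 are affected. Co-primary error and power are not. It should be corrected before any Part 2 analysis.

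**What to change.** In the SAP 6.4.3 table, make the superiority rows conditional on HA1 and HA2 both being met, and the 'super' superiority rows conditional on HA3 and HA4 both being met. Where the condition fails, print the highest conclusion still permitted:

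- GMR row 3 or 4 with SRR row 1: noninferiority on GMR only; superiority not tested.
- SRR row 3 or 4 with GMR row 1: noninferiority on SRR only; superiority not tested.
- GMR row 4 with SRR row 2: superiority on GMR; 'super' superiority not tested.
- SRR row 4 with GMR row 2: superiority on SRR; 'super' superiority not tested.

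A single sentence above the table making those rows subject to 6.4.2 would also remove the contradiction, but it leaves the author to work out what to report in the six cases.

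The cost is wording in one table. Section 6.4.2, Protocol 9.5.1, the hypotheses, margins, sample size and data collection stay as they are. Power under 6.4.2 does not change: for HA4 at the planning point, the chance that the SRR lower limit exceeds 0 stays at 65-74% with 250 adults and 86-93% with 1,000.

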6.4.4. Secondary Analysis of Antibody-Mediated Immunogenicity Endpoints

The following secondary immunogenicity evaluations will be performed.

- For each group in Part 1, GM level of SARS-CoV-2-specific serum Ab with corresponding 95% CI will be provided at each time point. The 95% CIs will be calculated based on the t-distribution of the log-transformed values then back transformed to the original scale for presentation. The following descriptive statistics will be also provided at each time point at which blood samples are collected for immunogenicity: the number of subjects (n), median, minimum and maximum.
- For Part 2, the immune response as measured by the serum Ab GM value and SRR against SARS-CoV-2 VOC (Omicron) at 28 days after the second dose will be compared to the serum Ab GM value and SRR at Day 57 (at 28 days after the second dose) against original strain after mRNA-1273 primary series in Study P301 using the same analysis methods described in Section 6.4.3.
- For Part 2, the immune response as measured by the serum Ab GM value and SRR against SARS-CoV-2 original strain at 28 days after the second dose will be compared to the serum Ab GM value and SRR at Day 57 (at 28 days after the second dose) against original strain after mRNA-1273 primary series in Study P301 using the same analysis methods described in Section 6.4.3.

6.4.5. Exploratory Analysis of Antibody-Mediated Immunogenicity Endpoints The below exploratory analyses of immunogenicity for Part 1 and/or Part 2 may be performed if applicable.

- GM level of SARS-CoV-2-specific bAb with corresponding 95% CI will be provided at each time point. The 95% CIs will be calculated based on the t-distribution of the log-transformed values then back transformed to the original scale for presentation. The following descriptive statistics will be also provided at each time point: the number of subjects (n), median, minimum and maximum.
- GM fold-rise (GMFR) of SARS-CoV-2-specific bAb levels with corresponding 95% CI will be provided at each postbaseline timepoint over pre-injection baseline at Day 1. The 95% CIs will be calculated based on the t-distribution of the log-transformed values then back transformed to the original scale for presentation. The following descriptive statistics will be also provided at each time point: the number of subjects (n), median, minimum and maximum.

Proportion of subjects with fold-rise ≥ 2 , and fold-rise ≥ 4 of serum SARS-CoV-2 specific bAb levels from Visit Day 1 (baseline) at each post injection time points will be tabulated with 2-sided 95% Clopper Pearson CIs.

- GMC of SARS-CoV-2-specific nAb concentrations with corresponding 95% CI will be provided at each time point using the same method mentioned above.
- GMFR of SARS-CoV-2-specific nAb concentrations with corresponding 95% CI will be provided at each postbaseline timepoint over pre-injection baseline at Day 1 using the same method mentioned above.

Proportion of subjects with fold-rise ≥ 2 , and fold-rise ≥ 4 of serum nAb from Visit Day 1 (baseline) at each post-injection time points will be tabulated with 2-sided 95% Clopper-Pearson CIs.

- Proportion of subjects with seroresponse due to vaccination will be tabulated with 2-sided 95% Clopper-Pearson CIs at each postbaseline timepoint. The definition of seroresponse can be found in Section 6.4.2.
- A plot to display the Ab value change from baseline to 28 days after the last dose in each vaccination group against the maternal factors (maternal COVID-19 vaccine status and maternal COVID-19 infection status) stratified by infant baseline SARS-CoV-2 status will be provided.

6.5. Efficacy Analysis

The exploratory analyses of the effectiveness in Part 2 will be performed primarily on the PP Set, unless specified otherwise. Analysis of effectiveness will be performed to evaluate the incidence rates of the following efficacy endpoints:

- COVID-19
- SARS-CoV-2 infection or COVID-19 regardless of symptomatology or severity
- Asymptomatic SARS-CoV-2 Infection

Subjects will be included in the treatment group to which they were randomized in Part 2.

Baseline SARS-CoV-2 status is described in Section 6.1. Baseline SARS-CoV-2 status, the serology test results at baseline, the RT-PCR test results at baseline will be summarized by treatment group.

Participants with baseline positive or missing SARS-CoV-2 status will be excluded from the PP Set.

In this study, the serology test results and the RT-PCR test results will be summarized by visit.

6.5.1. Endpoint Definition/Derivation

6.5.1.1. CDC Case Definition of COVID-19

The incidence of the first occurrence of COVID-19 postbaseline, where COVID-19 is defined as symptomatic disease based on CDC case definition, starting 14 days after each injection of mRNA-1273.214, will be summarized using incidence rate (number of cases divided by the total person-time).

Cases are defined as participants meeting clinical criteria based on both symptoms for COVID-19 and positive RT-PCR test results.

A positive PCR result of the eligible symptoms are summarized below in Table 1.

Table 1 Derivation for CDC Case Definition of COVID-19

	COVID-19
Postbaseline PCR results	Positive, AND
Systemic Symptoms	at least ONE of the following systemic symptoms: Fever (temperature $\geq 38^{\circ}$ C/ $\geq 100.4^{\circ}$ F) or chills (of any duration, including ≤ 48 hours), fatigue, headache, myalgia, nasal congestion or rhinorrhea, new loss of taste or smell, sore throat, abdominal pain, diarrhea, nausea/vomiting, poor appetite/poor feeding; OR
Respiratory symptoms	at least ONE of the following respiratory signs/symptoms: cough (of any duration, including ≤ 48 hours), shortness of breath or difficulty breathing (of any duration, including ≤ 48 hours).

The date of documented CDC Case Definition of COVID-19 (case) will be the later date of ([systemic symptom reported, or respiratory symptom reported] and, [date of positive PCR test]). Specifically, the date of documented CDC Case Definition of COVID-19 will be the

later date of the following two dates (date of positive PCR test, and the date of eligible symptom(s)), and the two dates should be within 14 days of each other.

- Date of positive PCR test,
- Date of eligible symptom(s), defined as earliest of
 - Respiratory symptom: earliest date of an eligible respiratory symptom is reported
 - Systemic symptoms: earliest date of the eligible systemic symptom is reported

The time to the first occurrence of CDC Case Definition of COVID-19 will be calculated as:

Time to the first occurrence of CDC Case Definition of COVID-19 = Date of documented CDC Case Definition of COVID-19 – Date of Randomization + 1.

COVID-19 will be assessed primarily for cases starting 14 days after second injection, i.e. date of documented COVID-19 – Date of the 2^{nd} injection \geq 14. COVID-19 may also be assessed for cases starting after first injection, 14 days after first injection, and starting after second injection.

6.5.1.2.SARS-CoV-2 Infection or COVID-19 regardless of symptomatology or severity

The incidence of SARS-CoV-2 infection starting 14 days after each injection of mRNA-1273.214 will be summarized using incidence rate (number of cases divided by the total person-time).

SARS-CoV-2 infection will be defined in participants with negative SARS-CoV-2 at baseline:

- Ab level against SARS-CoV-2 nucleocapsid protein that is negative at Day 1, but becomes positive (as measured by ligand-binding assay) postbaseline, OR
- Positive RT-PCR postbaseline.

Derivation of SARS-CoV-2 Infection is summarized in Table 2 below.

Table 2 Derivation for SARS-CoV-2 Infection

	Postbaseline assessments	

Baseline SARS- CoV-2 Status		bAb levels against SARS-CoV-2	Endpoint: SARS-CoV-2
	PCR test post baseline	Nucleocapsid	infection
	Positive (either at nasal swab test, or at symptom-prompt		
Negative at Baseline	nasal swab test)		Case
		Positive (at Post	
		baseline visit or	
		later) as measured	
		by ligand-binding	
Negative at Baseline		assay	Case

The incidence rate will be calculated as the number of cases divided by the total persontime.

The date of documented infection will be the earlier of:

- Date of positive postbaseline RT-PCR result, or
- Date of positive serology test result based on bAb specific to SARS-CoV-2 nucleocapsid

Time to the First SARS-CoV-2 infection = Date of the First documented infection - Date of randomization + 1.

SARS-CoV-2 infection regardless of symptomatology and severity will be assessed primarily for cases starting 14 days after second injection. SARS-CoV-2 infection may also be assessed for cases starting after first injection, 14 days after first injection, and starting after second injection.

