7. DELAY OR DISCONTINUATION OF STUDY INTERVENTION AND PARTICIPANT DISCONTINUATION/WITHDRAWAL

7.1. Criteria for Delay of Vaccine Administration

7.1.1. Individual Participant Criteria for Delay of Study Vaccination

Body temperature must be measured on dosing visits before vaccine administration (body temperature must be measured via the axillary route and any axillary reading of ≥ 37.8°C/≥ 100°F may be confirmed by a rectal measurement). The following events constitute criteria for delay of injection, and if any of these events occur at the time scheduled for dosing, the participant may receive the study injection at a later date within the time window specified in the SoA (Table 1), or the participant may be discontinued from dosing at the discretion of the investigator (Section 7.2):

- Acute moderate or severe infection with or without fever at the time of dosing
- Fever, defined as body temperature $\geq 38.0^{\circ}\text{C}/\geq 100.4^{\circ}\text{F}$ at the time of dosing

Participants with a minor illness without fever, as assessed by the investigator, can be vaccinated.

Participants with a fever of $\geq 38.0^{\circ}\text{C}/\geq 100.4^{\circ}\text{F}$ will be contacted within the time window acceptable for participation and re-evaluated for eligibility. If the investigator determines that the participant's health on the day of dosing temporarily precludes injection, the visit should be rescheduled within the allowed interval for that visit.

If a participant was exposed to a household contact (excluding school or other exposures) who tested positive for SARS-CoV-2 after the participant received the first dose, the administration of the second dose may be delayed to allow for at least 14 days between the positive test or the last day of symptoms (if present) of the household contact and Dose 2 as long as the participant remains asymptomatic.

If a participant tests positive for SARS-CoV-2 after having received Dose 1 but remains asymptomatic and the second dose is due before 14 days after the positive test, administration of the second dose may be delayed to allow for at least 14 days between the participant's positive test and Dose 2 as long as participant remains asymptomatic.

If a participant tests positive for SARS-CoV-2 after having received Dose 1 and develops symptoms of COVID-19, the participant may still receive a second dose, but the second dose should be delayed until approximately 90 days after diagnosis with COVID-19.

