5.5. Per-Protocol (PP) Set

The Per-protocol (PP) Set consists of all participants in the FAS who meet all the following criteria:

- a) Received planned doses of IP per schedule
- b) Had no major protocol deviations that impact key or critical data
- c) Had a negative RT-PCR test for SARS-CoV-2 and negative serology test based on bAb specific to SARS-CoV-2 nucleocapsid protein at baseline

The PP Set will be used as the primary analysis population in the efficacy analyses unless otherwise specified. Participants will be analyzed according to the treatment group to which they were randomized in Part 2.

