6.5.3. Sensitivity and Subgroup Analysis

Sensitivity analysis for key efficacy endpoints will be performed with the same methods described above based on the mITT Set and mITT-1 Set, with cases counted starting from randomization in Part 2. A sensitivity analysis will be performed based on a modified version of the endpoint definition, including COVID-19 non-RT-PCR tests.

Subgroup analysis may be done for the following subgroups:

- Sex (male, female)
- SARS-CoV-2 status at baseline
- Maternal COVID-19 vaccine status
- Maternal COVID-19 infection status
- Breastfeeding history
- Race
- Ethnicity

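### COVID-19 counts that start before Dose 2 are run mainly on the PP Set, and nearly all symptomatic between-dose cases drop out of that set unless a protocol-directed delay of Dose 2 counts as on schedule

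*SAP*

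**What the plan says.** **Counting windows.** SAP 6.5.1.1 opens by saying that first COVID-19 occurrence "starting 14 days after each injection of mRNA-1273.214, will be summarized using incidence rate (number of cases divided by the total person-time"). Later in the same section, "COVID-19 will be assessed primarily for cases starting 14 days after second injection", and "COVID-19 may also be assessed for cases starting after first injection, 14 days after first injection, and starting after second injection". SAP 6.5.1.2 has the same structure for SARS-CoV-2 infection. SAP 6.5.1.3 places asymptomatic infection 14 days after the second injection, again with optional earlier starts.

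**Analysis set.** SAP 6.5: "The exploratory analyses of the effectiveness in Part 2 will be performed primarily on the PP Set, unless specified otherwise". Criterion (a) of the PP Set in SAP 5.5 is "Received planned doses of IP per schedule". No day limits are attached to it.

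**Dosing after a positive test.** Under Protocol 7.1.1, if an infant tests positive after Dose 1 and develops symptoms, "the second dose should be delayed until approximately 90 days after diagnosis with COVID-19". An infant who tests positive but stays asymptomatic may have Dose 2 delayed so that at least 14 days separate the test and the dose.

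**Person-time and supporting analyses.** SAP 6.5.2 starts person-time at randomization, and gives numbers and percentages of cases on the PP Set and the FAS. SAP 6.5.3 repeats the key analyses "based on the mITT Set and mITT-1 Set, with cases counted starting from randomization in Part 2".

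**The concern.** Membership of the PP Set is settled at Dose 2, but some of the planned counts start at or soon after Dose 1. If symptomatic COVID-19 between the doses pushes Dose 2 off schedule, the event being counted takes the infant out of the set. The event-free infants stay in and contribute about 56 days of person-time in which almost no symptomatic case can be recorded. That is selection on the outcome, and it biases the incidence rate downward.

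Asymptomatic infections are much less affected because their delay is shorter. The infection endpoint counted from Dose 1 would therefore lose mainly its symptomatic component.

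At stake are the absolute rates in each arm and any information about protection between the doses. If one dose protected some infants, the placebo infants whose cases would show it would largely be missing from the main set.

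**Working it through.** The plan states no figure for this point, so there is none to reproduce. The calendar is consistent: 1 + 56 = Day 57 (Dose 2) and 57 + 365 = Day 422 (last visit).

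**Step 1. Latest permitted Dose 2.** Protocol 4.1.1.2 gives Day 57 with −14/+7 days, so Day 64 at the latest. The extended window there is +14 days, Day 71. Protocol 7.4 allows +21 days in a study pause, Day 78.

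**Step 2. Dose 2 after a symptomatic diagnosis on day d.** Dose 2 falls at about d + 90.

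| Diagnosis | Dose 2 at about | Past Day 64 | Past Day 71 | Past Day 78 |
|---|---|---|---|---|
| Day 2 | Day 92 | 28 days | 21 days | 14 days |
| Day 15 | Day 105 | 41 days | 34 days | 27 days |
| Day 56 | Day 146 | 82 days | 75 days | 68 days |

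No between-dose diagnosis day fits any stated window. In the most favourable row, Day 2 with the pause limit, the delay could be at most 78 − 2 = 76 days. An infant who never receives Dose 2 also fails the PP criterion.

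**Step 3. Asymptomatic positives.** With a 14-day delay, a test up to Day 64 − 14 = Day 50 still fits the standard window. The corresponding days are 57 (extended) and 64 (pause). Most of these infants can stay in the PP Set.

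**Step 4. Share of cases lost.** Assume a constant low hazard, nominal visits, follow-up to Day 422 and loss of all symptomatic between-dose cases.

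- Counted from 14 days after Dose 1 (Day 15): (57 − 15)/(422 − 15) = 42/407 = 10.3%.
- Counted from Dose 1 (Day 1): (57 − 1)/(422 − 1) = 56/421 = 13.3%. The PP rate is then 365/421 = 0.87 of the true rate.
- An earlier data cutoff makes this worse for the count from Dose 1: 180/236 = 0.76 at Day 237 and 28/84 = 0.33 at Day 85.

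**Step 5. Case numbers.** The documents give no attack rate, so a range is assumed. With 300 × 0.85 = 255 baseline-negative infants per arm, 12-month attack rate a and hazard h = −ln(1 − a)/365, the expected between-dose cases are 255 × (1 − e^(−56h)).

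| Assumed a | Between-dose cases per arm | Of these, from Day 15 | Share of all cases to Day 422 | PP rate / true rate from Dose 1 |
|---|---|---|---|---|
| 5% | 2.0 | 1.5 | 13.6% | 0.86 |
| 10% | 4.1 | 3.1 | 14.0% | 0.86 |
| 20% | 8.6 | 6.4 | 14.8% | 0.85 |
| 30% | 13.6 | 10.1 | 15.8% | 0.85 |

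On a set that does not require Dose 2, such as the mITT Set, the ratio in the last column is 1.00.

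**The case against.** Five points can be made against this, and most of them limit its size.

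1. *The affected counts are secondary.* The primary window starts 14 days after Dose 2, and SAP 6.5.1.1 makes counts from Dose 1 optional. This stands in part. The opening sentences of SAP 6.5.1.1 and 6.5.1.2 still commit to a summary from 14 days after each injection, so the sections pull two ways.
2. *The remedy is largely planned.* The mITT and mITT-1 analyses count from randomization. Randomization and Dose 1 are both on Day 1, so this is in effect the count from Dose 1, and it retains the between-dose cases. This stands. Still missing is an incidence rate from 14 days after Dose 1 on either set. The FAS is named only for numbers and percentages, and it includes baseline-positive infants.
3. *On schedule is undefined.* The delay is the protocol's own instruction, so it could be treated as compliant. SAP 6.2.6 leaves the major-deviation rules to a separate document finalized before database lock. This stands as an open reading, but neither document adopts it.
4. *The loss is not total.* The 90-day rule is a recommendation with an approximate interval. An infant with a minor afebrile illness whose pre-dose Day 57 swab is reported after dosing would stay on schedule. This stands: the loss is nearly all symptomatic between-dose cases, not every one.
5. *The percentages rest on assumptions.* This stands. The hazard and follow-up are assumed.

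A reader might go further and infer that every rate starting at or after Dose 1 is too low. The documents do not support that. Counts starting after Dose 2 lose no case through this mechanism among infants dosed on schedule. Nor does the SAP specify a rate confined to the interval between doses: its windows have start points but no stop at Dose 2.

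**Conclusion.** The point holds for symptomatic cases in counts that start before Dose 2, provided a Dose 2 delayed under Protocol 7.1.1 is not counted as on schedule. The SAP is silent on that. On this reading the PP rates are biased low by about 10% (from 14 days after Dose 1) to 13% (from Dose 1), assuming a constant low hazard, nominal visits and follow-up to Day 422. At assumed 12-month attack rates of 5% to 30%, this is about 2 to 14 between-dose cases per arm. The asymptomatic endpoint is much less affected.

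The consequence is modest. The endpoints are exploratory, no hypothesis or sample size depends on them, and the primary window is untouched. It would be tempting to conclude that the plan cannot describe incidence after the first dose. It can, through the mITT and mITT-1 analyses from randomization. The defect is that the set named as main for these counts is the one that selects on the outcome, and the start at 14 days after Dose 1 has no incidence rate on a set free of that selection. It is worth correcting before database lock if the Part 2 analyses are run.

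**What to change.** - In SAP 6.5.1 and 6.5.2, make the mITT Set (baseline-negative, at least one injection, as randomized) the main set for every count that starts before Dose 2, including the one from 14 days after Dose 1.
- Keep the PP Set for counts that start after Dose 2, including the primary window.
- In SAP 5.5, state whether a Dose 2 delayed under Protocol 7.1.1 satisfies criterion (a). SAP 5.7 uses the same criterion for the PPIS, so the definition should be checked there too.
- In SAP 6.5.1.1 and 6.5.1.2, settle whether the count from 14 days after Dose 1 is planned or optional.

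The cost is a few sentences in the SAP and a different population flag in the existing program. The mITT Set is already defined, no new data are needed, and no dosing rule changes.
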